Cover Page

Study Title: Twitter and Cardiovascular Health

NCT: NCT02806700

PI: [name] MD

University of Pennsylvania

Re: Study Protocol

Last update 4.10.2018

Study Protocol (Twitter and Cardiovascular Health:Twitter and Diabetes)
submitted prior to data analysis or un-blinding

Background

Cardiovascular (CV) disease remains the leading cause of morbidity and mortality in the US and is associated with significant economic burden. To advance against this major public health problem, the American Heart Association (AHA) and others have identified the need for a targeted focus on improving the CV health of populations, emphasizing “an array of new tools and competencies for implementing public health policy and population- and community-level interventions to complement the traditional, predominantly medically oriented interventions that have been promoted successfully in the past.” Social media channels like Twitter offer a new opportunity to explore health related communication generated by the public and for the public.

While effective therapies are available for diabetes mellitus (DM), disease management is often poor. Outcomes are often determined by patient activities outside of the clinical encounter such as diet, exercise, symptom monitoring, and medication adherence. Several approaches (e.g. self-care courses, home tele-monitoring) have been tested for aiding patients but are often resource intensive, and effectiveness trials have had varied results. Strategies with targeted text messaging, however, have shown promising results for improving clinical outcomes, patient satisfaction, improving health care utilization, and reducing healthcare costs.

Objective

For this study we seek to use Twitter, a public online platform to deliver health content over 6 months to participants with self-reported diabetes and evaluate the potential impact of this messaging on patient activation (a patients’ reported ability and willingness to take on the role of managing their health and healthcare).

Methods

We will identify participants with self-reported diabetes online. Participants will be identified through: self report on Twitter (e.g. “I have diabetes”), use of diabetes related hashtags and keywords on Twitter, ads posted online (e.g. Google, Reddit). Potential participants will then be “followed” on Twitter and privately direct messaged with a link to the study website. Ads would similarly include a link to the study website.

Individuals clicking on the study website would be directed to complete eligibility assessment questions. Eligibility questions include: age >21, self-report of diabetes, not pregnant (self-report), US residency.

Eligible patients who consent to participate would then complete a baseline survey and then be randomized to the control or intervention group.

Survey compensation of a \$25 dollar gift card would be provided for completion of the final survey at 6 months. Baseline and follow-up surveys will include questions regarding patient activation (PAM-13), self-rated health (SF-1), ideal CV health (BRFSS), self-care practices for DM (Summary of Diabetes Self-Care Activities Measure). To assess technology use, we will also ask questions from the *Perceived usefulness*, and *Perceived ease of use* surveys.

Control: The control group study participation would include completing a baseline survey and survey 6 months later.

Intervention: Participants randomized to the intervention group will be asked to “follow” the study team (e.g. @study handle). Once participants are “following” the study team, participants would receive 3x per week private messages via Twitter about heart health.

Twitter heart health messages will be identified via an automated program, which locates highly shared (i.e. retweets) tweets which contain the keyword “diabetes.” The 50 most retweeted in a given day (with a minimum 6 hour lag time to accumulate retweets) would then be curated by our team and 3 would be shared with participants 3x a week. We will use hand coding to describe themes associated with the curated tweets displayed to participants.

Outcome measure: The primary outcome measure will be patient activation measured by the PAM (a measure of behavior change and has been shown to be changeable over time). Predictor variables will include demographic variables (gender, age, race/ethnicity, and geographic region of residence), SF1, HbA1c. The secondary outcome will be change in self-reported HbA1c.

Sample size: Sample size estimates are based on the PAM measure. Assuming a 2-3 point change in the index PAM score (average 58) we estimate requiring 75 patients per arm to allow detection of this difference with 90% power and a type I error rate of 5%. We assume potentially 30% over-enrollment for loss to follow-up for a Twitter intervention.

Data Analysis: We will use summary statistics to compare demographics and survey responses (health status, ideal CV health status, self-practices) across groups. Summary statistics will be used to present data from the Perceived usefulness and Perceived ease of use measures for the intervention group.

For the primary outcome measure, we will use paired t-test for pre-post differences of PAM scores. In addition, multivariable linear regression models will be used to model change in PAM score with adjustment for demographic and baseline health characteristics not evenly distributed by arm. In all models, a binary indicator for control/intervention group will be included. Baseline PAM score will also be adjusted for in the model. Covariates with missing data will be assessed for patterns of missingness and non-ignorability and will be multiply imputed if deemed necessary and reasonable.

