Cover Page

Study Title: Twitter and Cardiovascular Health

NCT: NCT02806700

PI: [name] MD

University of Pennsylvania

Re: Statistical analysis plan

Last update 4.10.2018

Statistical Analysis Plan (Twitter and Cardiovascular Health:Twitter and Diabetes)

We will use summary statistics to compare demographics and survey responses (health status, ideal CV health status, self-practices) across groups. Summary statistics will be used to present data from the Perceived usefulness and Perceived ease of use measures for the intervention group.

For the primary and secondary outcome measures, we will use paired t-test for pre-post differences of scores. In addition, multivariable linear regression models will be used to model change in PAM score with adjustment for demographic and baseline health characteristics not evenly distributed by arm. In all models, a binary indicator for control/intervention group will be included. Baseline PAM score will also be adjusted for in the model. Covariates with missing data will be assessed for patterns of missingness and non-ignorability and will be multiply imputed if deemed necessary and reasonable.

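### Does giving one sample size and one power for a 2-3 point PAM change, with no SD or named test, undermine the trial's power claim?

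*Protocol*

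**What the plan says.** The sample-size paragraph in the protocol's Methods opens with "Sample size estimates are based on the PAM measure". It continues: "Assuming a 2-3 point change in the index PAM score (average 58) we estimate requiring 75 patients per arm". The stated power is 90% and the stated type I error is 5%. The paragraph then allows 30% over-enrolment for loss to follow-up, so 75 is best read as completers per arm. No SD, correlation, sidedness or test is given there, and the SAP does not discuss sample size.

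The tests appear elsewhere. The protocol's Data Analysis section says "For the primary outcome measure, we will use paired t-test for pre-post differences of PAM scores", and the SAP extends this: "For the primary and secondary outcome measures, we will use paired t-test for pre-post differences of scores". Both add a regression of change in PAM. For that model the protocol says "In all models, a binary indicator for control/intervention group will be included" and "Baseline PAM score will also be adjusted for in the model". The Objective is to "evaluate the potential impact of this messaging on patient activation", which in a randomised two-arm trial is the contrast between arms.

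**The concern.** Three features of the paragraph invite doubt.

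- A single n and a single power are attached to a range of effects. The required n varies with the inverse square of the effect, so 75 cannot be the exact requirement at both ends.
- The one PAM summary offered is a mean, which plays no part in sizing a difference. The quantity that does, an SD, is absent.
- The target could be a change within an arm or a difference between arms, and the analysis text names a test for each.

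At stake is how a null result would be read. If 90% was worked out for the within-arm paired test, or for the upper end of the range only, the comparison between arms could have clearly less power at 2 points than a reader would suppose.

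**Working it through.** **Inputs.** From the protocol's sample-size paragraph: 75 per arm, 90% power, 5% type I error, 2 to 3 points. Assumed: two-sided test, 75 completers per arm, and a regression with the arm indicator and baseline PAM only (df = 150 - 3 = 147). The protocol also allows adjustment for other characteristics that turn out unbalanced. These are unknown in advance, so the limits below are approximate for the full model.

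**Reproducing the 75.** This cannot be done forwards without an SD. The calculation has to run backwards, to the SD at which 75 per arm gives 90% power.

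**Arm term.** By normal approximation, the detectable standardised difference is (1.960 + 1.282) × √(2/75) = 0.529. With the noncentral t on 147 df it is 0.5328. The largest residual SD is then:
- 2 points: 2 / 0.5328 = 3.75
- 3 points: 3 / 0.5328 = 5.63

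For a one-sided 5% test the standardised difference is 0.4801, giving 2 / 0.4801 = 4.17 and 3 / 0.4801 = 6.25.

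**Paired test in one arm of 75 (df 74).** The detectable standardised change is 0.3793, so the largest SD of change is 2 / 0.3793 = 5.27 or 3 / 0.3793 = 7.91.

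**One n for a range.** The ratio of required n is (3/2)² = 2.25. With df = 2n - 3:
- If 75 is for 2 points, 3 points is 0.799 residual SD and needs 34 per arm.
- If 75 is for 3 points, 2 points is 0.355 residual SD and needs 168 per arm.

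**Power of the arm term under each basis for the 75:**

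| 75 sized on | Power at 2 points | Power at 3 points |
|---|---|---|
| Arm difference of 2 points (residual SD 3.75) | 90% | 99.8% |
| Arm difference of 2.5 points (residual SD 2.5 / 0.5328 = 4.69) | 74% | 97% |
| Arm difference of 3 points (residual SD 5.63) | 58% | 90% |
| Paired change of 2 points | 68-76% | 95-98% |
| Paired change of 3 points | 37-43% | 68-76% |

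The paired rows assume equal pre and post SDs and a pre-post correlation r from 0.8 (lower power) to 0.5 (higher). They use residual SD = SD of change × √((1 + r)/2). The documents give no value of r.

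**What the regression will deliver anyway.** With 75 completers per arm, the 95% confidence interval for the arm difference has half-width t(0.975, 147) × √(2/75) = 0.323 residual SD.

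**The case for a change.** The strongest case for a change is that the trial's question is the arm contrast, while the test named first for the primary outcome is a paired one. If the 75 came from that paired test, the arm term falls below 90% power at the same difference for any r above 2 × (0.3793 / 0.5328)² - 1 = 0.013, which is nearly any realistic correlation. Stating the inputs takes a few sentences. A residual SD pooled over arms could be obtained before unblinding and compared with 3.75 and 5.63.

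The first part stands as a description of what the text leaves open. It does not show that the paired basis was used. The wording, which speaks of detecting a difference with a number per arm, fits a comparison between arms equally well. Whether a paired test answers the objective is a separate question about the analysis, and printing an SD in the sample-size paragraph would not settle it.

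The pooled check is weaker than it looks. Leaving out the arm inflates the SD by √(1 + δ²/4), where δ is the true difference in residual SDs. That is 3.5% at δ = 0.5328. With a residual SD of 3.75 and a true difference of 3 points, δ is 0.80 and the inflation is 7.7%, so the pooled value is about 3.75 × 1.077 = 4.04. It would fail the 2-point limit although that limit is met. Sampling error in the SD adds to this. Whatever the check showed, it would set no new target.

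Nor can the sponsor simply be told to declare that the power refers to the arm term. If the 75 was in fact sized on the paired test, that statement would be false.

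**Conclusion.** The omission is real but is one of reporting. Without an SD, sidedness or test the 75 cannot be verified, and nothing in the documents shows it to be wrong. On one ordinary reading, sizing between arms at the lower end, the claim of 90% power is true throughout the 2-3 point range. On other readings the arm term has less, down to 37% at 2 points in the least favourable case tabulated, but those figures rest on a guessed sizing basis and, for the paired rows, on assumed correlations.

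Filling the gap would leave enrolment, tests and model as they are. The planned model already contains the arm indicator and baseline PAM, and a competent analyst will report that coefficient with its 95% interval. A null result should be read from the interval, whatever planning SD was used. For orientation, 75 completers per arm detect about 0.53 residual SD with 90% power (two-sided 5%, baseline PAM as the only covariate). No change to the plan is called for.

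### The primary PAM outcome is assigned a paired pre-post t-test with no arm term, the arm regression is not named as deciding, and HbA1c has no between-arm test

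*Protocol*

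**What the plan says.** The Protocol's Objective is to evaluate the effect of the messaging on patient activation, and its Methods randomise participants to control or intervention.

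- **Primary outcome, PAM.** The Protocol (Data Analysis) says "For the primary outcome measure, we will use paired t-test for pre-post differences of PAM scores". The SAP says "For the primary and secondary outcome measures, we will use paired t-test for pre-post differences of scores". Neither says whether the paired test is run in each arm or on both arms pooled.
- **Regression.** Both documents then introduce a second analysis: "In addition, multivariable linear regression models will be used to model change in PAM score". Apart from baseline PAM, which both include, its covariates are left to the observed imbalance: "with adjustment for demographic and baseline health characteristics not evenly distributed by arm". On the arm term, both say "In all models, a binary indicator for control/intervention group will be included".
- **Secondary outcome.** The Protocol (Outcome measure) says "The secondary outcome will be change in self-reported HbA1c". Its Data Analysis section names no test for this outcome. The SAP names only the paired t-test.
- **Predictors.** The Protocol (Outcome measure) already gives a list: "Predictor variables will include demographic variables (gender, age, race/ethnicity, and geographic region of residence), SF1, HbA1c".
- **Sample size.** For a change of 2 to 3 PAM points, "we estimate requiring 75 patients per arm to allow detection of this difference with 90% power" at a 5% type I error rate. No SD, pre-post correlation or sidedness is given, and the text does not say whether the 2 to 3 points are a change within an arm or a difference between arms.

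**The concern.** The effect of the messaging is a difference between randomised arms. A paired test asks whether PAM moved between baseline and 6 months, which is another question. Scores can move in both arms because the survey is repeated, through regression to the mean, or through secular change. If efficacy were read from the paired test, any such shared movement would count as a message effect, and the control arm would play no part in the inference.

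For PAM, the plan holds two analyses that answer different questions and no rule for which one prevails if they disagree. The wording ties the primary outcome to the one without an arm term. The regression's remaining covariates also depend on which baseline characteristics turn out unbalanced, so the model is not fully fixed in advance.

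For HbA1c the gap is wider, because no between-arm analysis is specified to fall back on.

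**Working it through.** **1. The text, by outcome**

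| Outcome | Protocol | SAP | Specified test comparing arms? |
|---|---|---|---|
| PAM | Paired t-test, plus regression with arm term | Same | Yes, but not designated as deciding |
| HbA1c change | No test named | Paired t-test only | No |

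The across-group summary statistics do not close the HbA1c gap. They list demographics, health status, ideal CV health status and self-practices, not HbA1c.

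**2. The plan's own figure**

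The 75 per arm cannot be reproduced, because no SD is stated. It can only be solved backwards (two-sided 5%, 90% power, noncentral t):

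- Two-sample test: 75 per arm detects a standardised difference of 0.533. The implied SD of change is 2/0.533 = 3.75 for 2 points and 3/0.533 = 5.63 for 3 points.
- Paired test within one arm: 75 detects 0.379. The implied SD is 2/0.379, about 5.27, for 2 points and 3/0.379, about 7.91, for 3 points.

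The documents do not say which of these was meant, so 75 is neither confirmed nor refuted.

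**3. Paired test when the messages do nothing**

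Assume no treatment effect, a rise d common to both arms, and an SD of change s. The paired test on n people is significant with probability P(|T| > t(0.975, n−1)), where T is noncentral t with n−1 degrees of freedom and noncentrality d√n/s. For n = 75, s = 8, d = 2, the noncentrality is 2 × 8.660/8 = 2.165 and the critical value is 1.993, which gives 0.570.

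| Common rise (points), s = 8 | 0 | 1 | 2 | 3 |
|---|---|---|---|---|
| Intervention arm only, n = 75 | 5% | 19% | 57% | 89% |
| Both arms pooled, n = 150 | 5% | 33% | 86% | >99% |
| Between-arm t-test | 5% | 5% | 5% | 5% |

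The common rise cancels from the between-arm difference. Simulation with 200,000 trials gave 0.049 to 0.050 at every rise.

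Range over the SD, intervention-arm test:

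| s | 1-point rise | 2-point rise |
|---|---|---|
| 3.75 | 63% | >99% |
| 5.63 | 33% | 86% |
| 8 | 19% | 57% |
| 10 | 14% | 40% |

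A milder misreading is to run the test in each arm and claim efficacy if the intervention arm is significant and control is not. With p from the first row of the s = 8 table, the probability is p(1−p): 0.188 × 0.812 = 0.15, 0.570 × 0.430 = 0.25 and 0.893 × 0.107 = 0.10 for rises of 1, 2 and 3 points.

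**4. What a between-arm primary does to power**

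- If 75 was sized for a two-arm difference (SD 3.75 or 5.63), the 90% stands.
- If it was sized for the paired test (SD 5.27 or 7.91), an unadjusted two-sample test at standardised difference 0.379 has noncentrality 0.379 × √(75/2) = 2.32. Power is about 64%, and 90% needs about 148 per arm.
- Baseline adjustment recovers part of this. With equal SDs at both times and correlation ρ, residual SD = SD of change × √((1+ρ)/2). At ρ = 0.5 the factor is 0.866: power about 76%, 111 per arm for 90%. At ρ = 0.7 it is 0.922: power about 71%, 126 per arm.

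**The case against.** The strongest reply is that PAM is already handled. The planned regression, with an arm indicator and baseline PAM, is a valid between-arm analysis, and the words introducing it need not rank it below the paired test. That stands in part: for PAM this is a missing designation, not a missing analysis. It does not remove the problem, because the primary outcome is attached by name to the test without an arm term and nothing says which result prevails.

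Second, the large percentages need someone to declare efficacy from one arm, or from both pooled, while ignoring the control arm and the regression. The documents do not say this will happen. That is fair. Those figures are a worst case under assumed SDs and drifts, and the per-arm misreading gives 10% to 25% at an SD of 8.

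Third, the fall to 64% power arises only if 75 was sized for a paired test, and a per-arm number fits a two-arm comparison at least as well. That also stands. It is a reason to state the SD, not evidence that 75 is wrong.

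Fourth, the listed predictors may be the pool from which unbalanced covariates are drawn, so the two passages need not conflict. Adjusting for the full list would also use several parameters, and HbA1c may be missing for some participants. The covariate point is therefore secondary.

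For HbA1c, the statement that all models carry an arm indicator could be stretched to cover it. But the only models described have change in PAM as outcome and adjust for baseline PAM.

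**Conclusion.** The concern holds, and the plan should be changed before it is used to judge efficacy. For HbA1c the SAP is wrong as written: followed literally, it yields a within-person change that cannot show an effect of the messaging. For PAM a suitable analysis is present but is not made the deciding one. Both conclusions rest on the text alone.

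The size of the consequence depends on assumptions. Over the SDs shown (3.75 to 10), a shared rise of 1 point makes a null intervention-arm paired test significant in 14% to 63% of trials, and a rise of 2 points in 40% to over 99%. With no shared change there is no inflation. The documents give no SD of change and no expected drift. The covariate and sample-size points are subordinate.

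**What to change.** Make the same changes in the Protocol and the SAP:

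1. State that the single primary result is the arm coefficient from the linear regression of change in PAM on randomised arm, adjusted for baseline PAM, with a 95% CI and a two-sided p-value at 0.05.
2. Fix any other covariates in advance, for example from the Protocol's own predictor list, instead of selecting them by observed imbalance. A shorter list is reasonable if missing data or the number of parameters is a worry.
3. Specify the same model for change in self-reported HbA1c, adjusted for baseline HbA1c.
4. Keep the paired t-tests as within-arm description, with no efficacy claim.
5. State the SD behind 75 per arm, and confirm or restate the 90% power for the between-arm comparison.

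The cost is a few sentences and one sample-size check. No data are needed beyond the baseline and 6-month values that the change outcomes already require. The drawback is that item 5 may show power below 90%. If enrolment has closed, the power can only be restated.

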Cover Page

Study Title: Twitter and Cardiovascular Health

NCT: NCT02806700

PI: [name] MD

University of Pennsylvania

Re: Statistical analysis plan

Last update 4.10.2018

Statistical Analysis Plan (Twitter and Cardiovascular Health:Twitter and Diabetes)

We will use summary statistics to compare demographics and survey responses (health status, ideal CV health status, self-practices) across groups. Summary statistics will be used to present data from the Perceived usefulness and Perceived ease of use measures for the intervention group.

For the primary and secondary outcome measures, we will use paired t-test for pre-post differences of scores. In addition, multivariable linear regression models will be used to model change in PAM score with adjustment for demographic and baseline health characteristics not evenly distributed by arm. In all models, a binary indicator for control/intervention group will be included. Baseline PAM score will also be adjusted for in the model. Covariates with missing data will be assessed for patterns of missingness and non-ignorability and will be multiply imputed if deemed necessary and reasonable.

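### The only analysis planned for the secondary outcome, self-reported HbA1c, is a pre-post test that does not compare the randomised arms

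*SAP*

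**What the plan says.** The Protocol's Outcome measure paragraph states: "The secondary outcome will be change in self-reported HbA1c". HbA1c is also listed there among the predictor variables. Both arms supply data at both times; of the control arm the Protocol says "The control group study participation would include completing a baseline survey and survey 6 months later".

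The SAP mentions the secondary outcome once: "For the primary and secondary outcome measures, we will use paired t-test for pre-post differences of scores". It does not say whether this test is run within each arm or on both arms pooled.

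The SAP then states that "multivariable linear regression models will be used to model change in PAM score", that "In all models, a binary indicator for control/intervention group will be included", and that "Baseline PAM score will also be adjusted for in the model". Across-group comparison outside the regression is descriptive: "We will use summary statistics to compare demographics and survey responses (health status, ideal CV health status, self-practices) across groups".

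The Protocol's Data Analysis section has the same regression text but a narrower paired test: "For the primary outcome measure, we will use paired t-test for pre-post differences of PAM scores". It states no analysis for HbA1c.

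**The concern.** Randomisation supports a comparison of arms, and the data for that comparison exist for HbA1c. The plan does not commit to making it. A paired test cannot separate an effect of messaging from any change that both arms share over 6 months.

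Two things are at stake. A significant paired result could be reported as evidence that messaging improved HbA1c when control participants changed just as much. And any between-arm estimate or confidence interval for HbA1c that is later reported would be an analysis outside the plan, with its model and covariates open to choice after the data are seen.

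**Working it through.** **Reading the text.** Each analysis in the two documents, and whether it gives an inferential arm comparison of HbA1c:

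| Analysis | Outcome named | Compares arms? | Covers HbA1c? |
|---|---|---|---|
| Paired t-test, SAP | Primary and secondary | No | Yes |
| Paired t-test, Protocol | PAM | No | No |
| Linear regression, both documents | Change in PAM | Yes, by arm term | No |
| Summary statistics, both documents | Demographics and survey responses | Descriptively | Not named |

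No row both covers HbA1c and tests the arm difference.

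**The plan's own figure.** The documents give no HbA1c effect size, SD or sample size. The 75 per arm in the Sample size paragraph is for PAM (2 to 3 points, 90% power, 5% type I error) and comes without an SD, so it cannot be reproduced. For a two-sided two-sample test it implies SD = d × √(n/2) / (1.960 + 1.282). That is 2 × 6.124 / 3.242 = 3.8 for 2 points and 3 × 6.124 / 3.242 = 5.7 for 3 points. None of this bears on HbA1c; 75 is borrowed below only as a working number.

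**What the paired test detects when messaging does nothing.** Assume the same mean change in both arms, δ, in units of the SD of the change. The paired t statistic has n − 1 degrees of freedom and noncentrality δ√n. The two-sided 5% critical values are 2.010 (n = 50), 1.993 (n = 75), 1.984 (n = 100) and 1.976 (n = 150).

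| Paired test | δ | δ√n | P(significant) |
|---|---|---|---|
| Intervention arm, n = 75 | 0.1 | 0.866 | 0.137 |
| Intervention arm, n = 75 | 0.2 | 1.732 | 0.401 |
| Intervention arm, n = 75 | 0.3 | 2.598 | 0.727 |
| Both arms pooled, n = 150 | 0.1 | 1.225 | 0.229 |
| Both arms pooled, n = 150 | 0.2 | 2.449 | 0.682 |
| Both arms pooled, n = 150 | 0.3 | 3.674 | 0.955 |
| Intervention arm, n = 50 | 0.2 | 1.414 | 0.284 |
| Intervention arm, n = 50 | 0.3 | 2.121 | 0.548 |
| Intervention arm, n = 100 | 0.2 | 2.000 | 0.508 |
| Intervention arm, n = 100 | 0.3 | 3.000 | 0.844 |

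**Between-arm test in the same setting.** The expected arm difference is δ − δ = 0, so the noncentrality is 0 and the rejection rate is 5% whatever δ is. Simulation with 75 per arm (40,000 trials at each of the three values of δ) gives about 5% each time. Baseline-adjusted regression (4,000 trials, assumed baseline to follow-up correlation 0.7) rejects in 4.9% and 5.4% at δ = 0.2 and 0.3.

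**Separate tests set side by side.** If the paired test is run in each arm and the verdicts are compared, the chance that only the intervention arm is significant is p(1 − p), where p is the within-arm probability above. At n = 75 this is 0.137 × 0.863 = 0.12, 0.401 × 0.599 = 0.24 and 0.727 × 0.273 = 0.20 at δ = 0.1, 0.2 and 0.3. The maximum is 0.25, at δ of about 0.23. Contrasting the two p-values is therefore not a 5% test of the arm difference either.

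**The case against.** The strongest textual reply is that the SAP says the arm indicator goes into all models, in the plural, which might take in HbA1c. It does not serve as a prespecification. The models just introduced are of change in PAM, the next sentence adjusts for baseline PAM, and a paired t-test has no place for an arm indicator. The same sentence stands in the Protocol, whose analysis text never mentions the secondary outcome. Different covariate sets for PAM would explain the plural.

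The bracketed list of survey responses may be illustrative, so a descriptive comparison of HbA1c across arms may be intended. That can be granted; it is still not inferential.

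Three further points stand in part:

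- The paired test is valid for its own null hypothesis. The percentages above are its power against a real common change, not its type I error. They become false claims only if the result is read as an effect of messaging, but it is the only HbA1c test the plan offers.
- Eligibility does not select on high HbA1c, so regression to the mean is only one possible source of common change and not one the entry criteria build in. The argument needs only some change shared by both arms, from whatever cause.
- HbA1c is a secondary outcome, and the primary outcome does have a baseline-adjusted arm comparison. The trial's main conclusion is not affected, which limits the weight of the point but does not remove it.

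**Conclusion.** The concern holds. Neither document prespecifies an inferential between-arm analysis for the only named secondary outcome, and the test the SAP does assign answers a different question, whether it is run within arm or pooled. This conclusion rests on the text alone.

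The size is illustrative. It rests on assumed common changes of 0.1 to 0.3 SD, no effect of messaging, and a PAM-based 75 per arm, because the number of participants with paired HbA1c values is not given. On those assumptions the intervention-arm test is significant in about 14% to 73% of trials and the pooled test in about 23% to 95.5%, against 5% for an arm comparison. With 50 to 100 per arm, the intervention-arm figure runs from 28% to 51% at 0.2 SD and from 55% to 84% at 0.3 SD. The plan should be corrected on this point, but the primary analysis is not at risk from it.

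**What to change.** In the SAP, state that HbA1c will be analysed by linear regression of the 6-month value (or the change) on randomised arm, adjusted for baseline HbA1c, with the arm difference and its 95% CI reported. State that the paired t-tests of HbA1c are descriptive and whether they are run by arm or pooled. Put a matching sentence in the Protocol's Data Analysis section, which now has none for this outcome.

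It would be sensible to say in the same place how missing HbA1c values are handled, since imputation is planned only for covariates.

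The cost is a short addition to each document and one more regression. No new data collection is implied: a change in HbA1c already needs both values, and HbA1c is already listed as a predictor. The survey contents listed in the Protocol do not name an HbA1c item, so the team should confirm that it is asked at both times.
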